**Note:**

- Subjects may return to clinic for an additional blood draw in-between the clinic visits for plasma HIV-1 RNA levels, per the discretion of the Investigator.
- Virologic failure is defined as two consecutive levels of  $\geq 200$  copies/mL.
  - Subjects in Group A that experience virologic failure have option of re-initiating ART regimen or participating in Part 2 of Treatment Phase and receive higher dose of PRO 140 (525mg SC) weekly injection for remainder of 48-week Treatment Phase or until subsequent virologic failure event after viral re-suppression on higher dose.
  - Subjects in Group B that experience virologic failure have option of re-initiating ART regimen or participating in Part 2 of Treatment Phase and receive higher dose of PRO 140 (700mg SC) weekly injection for remainder of 48-week Treatment Phase or until subsequent virologic failure event after viral re-suppression on higher dose.
- Subjects who meet any criteria (other than virologic failure) for discontinuation of study treatment as specified in [Section 5.2.1](#) of the protocol, will undergo T48 Visit assessments and enter the Follow-up Phase of the study.
- Subjects who do not experience virologic failure will enter the Follow-up Phase of the study at the end of 48-week Treatment Phase.

Visits during the Treatment Phase will commence on T1, i.e. the date of first treatment, with weekly visits ( $\pm 3$  days) thereafter. The first Treatment Visit (T1) will take place as soon as HIV-

1 viral tropism, genotype and phenotype resistance results are available for review by Investigator, within 6 weeks of the Screening Visit.

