7.5.5 Time to Virologic Failure

The date of virologic failure is defined as the date of the second assessment of the two (2) consecutive plasma HIV-1 RNA levels of ≥ 200 copies/mL when virologic failure is confirmed.

For the censored subjects (i.e., subjects who do not have an event) the date of event will be:

- The time of the last visit data; if the subject completes the trial;

- The time of the early termination for those subjects who withdraw or early terminate from the trial.

[for those with virologic failure]

Time to virologic failure = (Date of first HIV-1 RNA levels of ≥ 200 copies/mL – Date of first treatment) +1

[for those without virologic failure]

Time to virologic failure = (Date of last visit/ early termination – Date of first treatment) +1

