7.5.6 Viral Re-suppression

For all subjects with virologic failure, viral re-suppression is defined as having a plasma HIV-1 RNA levels of <50 copies/mL after experiencing virologic failure.

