7.5.7 Time to Viral re-suppression

This will be assessed for all subjects experiencing virologic failure. The date of viral re-suppression is defined as the date of first assessment where plasma HIV-1 RNA levels of <50 copies/mL after virologic failure.

Time to viral re-suppression = (Date of first HIV-1 RNA levels of < 50 copies/mL – Date of virologic failure) +1

7.5.8 Time to Viral re-suppression after re-initiation of oral combination antiretroviral regimen (Re-ART)

This will be assessed for all subjects experiencing virologic failure and oral combination antiviral therapy is re-initiated. The date of viral re-suppression is defined as the date of first assessment where plasma HIV-1 RNA levels of <50 copies/mL after virologic failure.

Time to viral re-suppression after Re-ART = (Date of first HIV-1 RNA levels of < 50 copies/mL – Date of first re-initiation of oral combination regimen) +1

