8.2.2.1 Proportion of participants experiencing virologic failure at the assigned dose

The percentages of subjects with virologic failure (as defined in [Section 7.5.6](#)) will be presented descriptively by treatment groups for the ITT and PP populations.

Note: Assigned dose refers to the dose allocated at the time of randomization/enrollment.

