8.2.2.3 Proportion of participants moved to rescue arm or higher dose group

The percentages of subjects moved to a rescue arm or higher dose will be presented descriptively by treatment groups for the ITT and PP populations.

Note: Rescue is defined as subjects who were unable to maintain viral suppression, or experienced virologic failure, and moved to a higher dose of PRO 140.

8.2.2.4 Proportion of participants achieving viral re-suppression (HIV-1 RNA <50 copies/mL) during Treatment Phase after moving to rescue arm or higher dose group

The percentages of subjects with virologic re-suppression (as defined in [Section 7.5.8](#)) will be presented descriptively by treatment groups for the subset of the ITT and PP populations that moved to a rescue arm or higher dose group.

8.2.2.5 Time to achieving viral re-suppression (HIV-1 RNA <50 copies/mL) during Treatment Phase for subjects who moved to rescue arm or higher dose group

The number of observations, mean, standard deviation, median, and minimum and maximum values will be presented to summarize time to viral re-suppression (as defined in [Section 7.5.9](#)) by treatment groups for the subset of the ITT and PP populations that moved to a rescue arm or higher dose group.

8.2.2.6 Proportion of participants achieving viral re-suppression (HIV-1 RNA <50 copies/mL) after experiencing virologic failure (during the Treatment and Follow-up Phase)

The percentages of subjects with virologic re-suppression (as defined in [Section 7.5.8](#)) will be presented descriptively by treatment groups for the subset of the ITT and PP populations that experienced virologic failure.

8.2.2.7 Time to achieving viral re-suppression (for virologic failure subjects) after re-initiation of oral combination antiretroviral regimen during the Follow-up Phase.

The number of observations, mean, standard deviation, median, and minimum and maximum values will be presented to summarize time to viral re-suppression after re-initiation of oral combination antiretroviral regimen (as defined in [Section 7.5.10](#)) by treatment groups for the subset of the ITT and PP populations that experienced virologic failure and had re-initiation of oral combination antiviral therapy.

8.2.2.8 Proportion of participants completing 24, 48 weeks of PRO 140 treatment with HIV-1 RNA <50 copies/mL

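### The rescue-dose re-suppression outcomes have no rescue-specific definition: both the counting window and the clock they rely on start at virologic failure, not at the first rescue injection

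*SAP*

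**What the plan says.** Two of the primary efficacy outcomes (Protocol 8.2.2; SAP 3.1.2) concern escalation: the proportion re-suppressed after moving to rescue, and the time to re-suppression in those subjects. SAP 8.2.2.4 and 8.2.2.5 present them "by treatment groups for the subset of the ITT and PP populations that moved to a rescue arm or higher dose group". The 8.2.2.4 heading limits the event to re-suppression "during Treatment Phase after moving to rescue arm or higher dose group". The 8.2.2.5 heading names the phase and the population but no starting date.

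For definitions, 8.2.2.4 points to 7.5.8 and 8.2.2.5 to 7.5.9. Section 7.5.8 is the time to re-suppression after ART is restarted, and there is no 7.5.9.

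The general definitions are in three places:

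- SAP 7.5.6: "viral re-suppression is defined as having a plasma HIV-1 RNA levels of <50 copies/mL after experiencing virologic failure".
- SAP 7.5.7: "Time to viral re-suppression = (Date of first HIV-1 RNA levels of < 50 copies/mL – Date of virologic failure) +1".
- SAP 7.5.5: "The date of virologic failure is defined as the date of the second assessment of the two (2) consecutive plasma HIV-1 RNA levels".

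For restarted ART, SAP 7.5.8 starts the clock at the date of re-initiation. The rescue dose has no counterpart.

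**The concern.** Outcomes meant to describe what happens on the higher dose should start when the higher dose starts. Under 7.5.6 and 7.5.7 both the window and the clock start at failure, which is a sampling date. The second RNA result is not known on that date. The subject must then elect Part 2 (Protocol synopsis and 4.2), dosing is weekly within 3 days either way, and no maximum interval to the first rescue injection is stated. Part of the reported time is therefore spent on the failed dose. How large a part depends on result turnaround and the subject's decision, not on drug effect.

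The window raises a second question: may a value below 50 drawn in that interval be scored as a rescue response? Two programmers could answer differently and produce different primary efficacy tables. Re-suppression after failure in general already has its own outcome, 8.2.2.6, so 8.2.2.4 and 8.2.2.5 add something distinct only if they isolate the rescue dose.

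**Working it through.** The plan gives no figure to reproduce, so this is a check of references and dates.

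**1. Which definitions apply.** In SAP 8.2.2 every pointer into 7.5 runs two too high. Failure is cited as 7.5.6 and defined in 7.5.4; time to failure is cited as 7.5.7 and defined in 7.5.5; time after ART restart is cited as 7.5.10 and defined in 7.5.8. Taking two off the pointers in 8.2.2.4 and 8.2.2.5 gives 7.5.6 and 7.5.7.

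**2. Size of the time difference.** Let V be the failure date, R the first rescue injection and S the first RNA below 50. For V, I use the worded definition in 7.5.5 (second value); the time-to-failure formula in that section uses the first value.

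- Reported time = S − V + 1
- Time on rescue = S − R + 1
- Difference = R − V, when S follows R

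With visit Tn on day 7(n − 1) + 1, and R − V assumed because the documents do not give it:

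| V | S | Reported (days) | On rescue, gap 0 | Gap 7 | Gap 14 | Gap 28 |
|---|---|---|---|---|---|---|
| T12, day 78 | T16, day 106 | 106 − 78 + 1 = 29 | 29 | 22 | 15 | 1* |
| T25, day 169 | T33, day 225 | 225 − 169 + 1 = 57 | 57 | 50 | 43 | 29 |

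*Here the sample falls on the day of the first rescue injection, so unless drawn after it, it is not a response on rescue.

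**3. Can a value fall in the gap?** Yes. Protocol 4.2 allows it: "Subjects may return to clinic for an additional blood draw in-between the clinic visits for plasma HIV-1 RNA levels". The schedule allows it too, since Protocol 7.10.9 samples RNA at both T16 and T17. Take failure confirmed at T16 (day 106), RNA below 50 at T17 (day 113), and a first rescue injection assumed at T18 (day 120). Read literally, 7.5.6 and 7.5.7 record a success at 113 − 106 + 1 = 8 days. From the rescue injection the figure is 113 − 120 + 1 = −6, so it is not a rescue event. If the first value below 50 on rescue came at day 148, the time would be 148 − 120 + 1 = 29 days on rescue, or 148 − 106 + 1 = 43 from failure. A gap value therefore shortens the recorded time.

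**4. How often, and with what effect on the proportion.** The documents give no frequency. Taking P(RNA < 50) = Φ((log10 50 − log10 level)/SD) with an assumed within-subject SD of 0.3 to 0.4 log10, one gap draw falls below 50 with this probability:

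| True level (copies/mL) | SD 0.3 | SD 0.4 |
|---|---|---|
| 150 | 0.056 | 0.116 |
| 200 | 0.022 | 0.066 |
| 400 | 0.001 | 0.012 |

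These apply only to subjects who have a gap draw. Let q be the share of all rescued subjects with a gap value below 50 and p the re-suppression rate on rescue among the others. In the worst case, subjects with a gap value never re-suppress on rescue. The literal proportion is then q + (1 − q)p, the rescue-only proportion is (1 − q)p, and the difference is q. With p assumed at 50%:

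| q | Literal | Rescue only |
|---|---|---|
| 0% | 50% | 50% |
| 2% | 51% | 49% |
| 5% | 52.5% | 47.5% |
| 10% | 55% | 45% |

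**5. Subjects with no clock.** The rescue definition in SAP 3.1.2 and 8.2.2.3 includes subjects who could not maintain suppression as an alternative to failure. Anyone moved without meeting failure has no V, so 7.5.7 gives no time, and 7.5.6 covers only subjects with failure.

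**The case against.** A reader might infer that the SAP has settled that values on the failed dose count as rescue successes. It has not. The 8.2.2.4 heading excludes them and the general definition in 7.5.6 admits them, so this is an unresolved conflict.

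The VF Visit, whose list includes RNA, is a doubtful source of gap draws. Protocol 4.3 addresses all failing subjects, but before Follow-up. The synopsis and 4.2 assign that visit to subjects not electing Part 2 and to Group C, and Section 4 exempts those opting into Part 2. That leaves investigator-requested draws and scheduled draws that happen to fall in the gap.

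A reader might also infer that every rescue time is too long. The excess is relative to time on the rescue dose, may be zero for some subjects, and reverses when a gap value is counted. Time from failure is a legitimate measure of a treatment strategy, which is what the objective names, and the 8.2.2.5 heading fixes no origin. The contrast with 7.5.8 is also imperfect: its clock starts at ART restart, but its event is still the first value below 50 after failure.

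Finally, SAP 7.4 plans no inferential statistics, all data are listed by subject, and exposure is already split by assigned and rescue dose (SAP 8.1.6). So no error rate is affected and either clock could be derived later. That limits the consequence. It does not remove the need to say which result is tabulated as the primary efficacy outcome.

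**Conclusion.** The point holds in this form: no definition serving 8.2.2.4 and 8.2.2.5 refers to the start of the rescue dose. Once the cross-references are corrected, the stated rule adds the failure-to-rescue interval to each rescue time when the event follows the first rescue injection. The size is that interval. The values 0, 7, 14 and 28 days are illustrations, and the documents support no particular one.

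Crediting a gap value is a possible literal reading that contradicts the outcome's own heading. It needs a fall from at least 200 to below 50 on a sample drawn before the first rescue injection, so it is probably uncommon; the percentages rest on an assumed SD and assumed RNA levels. Subjects moved to rescue without meeting failure, if there are any, are left without a clock.

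**What to change.** Add a rescue-specific definition to SAP 7.5 and cite it in 8.2.2.4 and 8.2.2.5:

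- **Event:** first RNA below 50 copies/mL from a sample drawn after the first rescue-dose injection, during the Treatment Phase, while on the rescue dose and before any ART re-initiation. The last condition must cover the end-of-treatment overlap. Protocol 4.2.3 restarts ART at Week 47 and RNA is drawn at T48, so limiting the event to the Treatment Phase would still credit a value obtained on ART.
- **Time:** (date of that sample − date of first rescue-dose injection) + 1. This also gives a clock to anyone moved without meeting failure.
- **Gap values:** tabulate separately subjects with RNA below 50 between failure and the first rescue injection, and do not credit these values to rescue.
- **Failure-date clock:** keep 7.5.6 and 7.5.7 as a separate summary of re-suppression after failure in general.
- **Cross-references:** correct the 7.5 pointers throughout 8.2.2.

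The cost is SAP wording and the matching programming. Rescue exposure, RNA dates and ART restart dates are already needed for SAP 8.1.6, 7.5.7 and 7.5.8. The stated rescue success proportion may fall slightly.

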3.1.2 Efficacy Outcome Measures

- Proportion of participants experiencing virologic failure at the assigned dose

Note: (1) Virologic failure is defined as two (2) consecutive plasma HIV-1 RNA levels of \geq 200 copies/mL. (2) Assigned dose refers to the dose allocated at the time of randomization/enrollment.

- Time to virologic failure at the assigned dose
- Proportion of participants moved to rescue arm or higher dose group

Note: Rescue is defined as subjects who were unable to maintain viral suppression, or experienced virologic failure, and moved to a higher dose of PRO 140

- Proportion of participants achieving viral re-suppression (HIV-1 RNA <50 copies/mL) during Treatment Phase after moving to rescue arm or higher dose group
- Time to achieving viral re-suppression (HIV-1 RNA <50 copies/mL) during Treatment Phase for subjects who moved to rescue arm or higher dose group

- Proportion of participants achieving viral re-suppression (HIV-1 RNA <50 copies/mL) after experiencing virologic failure (during the Treatment and Follow-up Phase)
- Time to achieving viral re-suppression (for virologic failure subjects) after re-initiation of oral combination antiretroviral regimen during the Follow-up Phase.
- Proportion of participants completing 24, 48 weeks of PRO 140 treatment with HIV-1 RNA <50 copies/mL
- Mean change in CD4 cell count, at each visit within the Treatment Phase
- To evaluate the prognostic factors of therapeutic success of PRO 140 monotherapy during the Treatment Phase.
 - CCR5 Receptor Occupancy
 - CCR5 Genotyping Status (heterozygotes or homozygotes)
 - gp120 genotyping
 - Baseline HIV-1 RNA Single Copy levels
 - Immune Activation Markers
 - PhenoSense® Entry Assay

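### Rescue re-suppression (SAP 8.2.2.4 and 8.2.2.5) has no definition tied to the first rescue dose, and the ART version in 7.5.8 can end before ART restarts

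*SAP*

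**What the plan says.** SAP 3.1.2 lists among the primary efficacy outcomes "Time to achieving viral re-suppression (HIV-1 RNA <50 copies/mL) during Treatment Phase for subjects who moved to rescue arm or higher dose group", together with the matching proportion. Sections 8.2.2.4 (proportion) and 8.2.2.5 (time) summarise them in the subset that moved up.

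The definitions are in SAP 7.5:

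- 7.5.6 requires one RNA value below 50 copies/mL at some point after failure.
- 7.5.7 fixes the end date: "The date of viral re-suppression is defined as the date of first assessment where plasma HIV-1 RNA levels of <50 copies/mL after virologic failure". The start is "Date of virologic failure) +1".
- 7.5.5 supplies the failure date: "The date of virologic failure is defined as the date of the second assessment of the two (2) consecutive plasma HIV-1 RNA levels".
- 7.5.8, for subjects who go back to ART, repeats the end date of 7.5.7 and starts at "Date of first re-initiation of oral combination regimen) +1".

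No formula in 7.5 uses the date of the first rescue dose. Section 8.2.2.5 plans summary statistics "to summarize time to viral re-suppression (as defined in [Section 7.5.9", but the SAP's numbering in 7.5 stops at 7.5.8.

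Two other statements matter. The rescue outcome in SAP 3.1.2 carries the note "Rescue is defined as subjects who were unable to maintain viral suppression, or experienced virologic failure", so confirmed failure is one of two listed routes. The notes in Protocol 4.2 add: "Subjects may return to clinic for an additional blood draw in-between the clinic visits for plasma HIV-1 RNA levels", at the Investigator's discretion.

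**The concern.** The titles of these outcomes concern what happens on the higher dose, or after ART restart. The definitions are anchored to virologic failure, which is a sampling date. A subject moves up only after that sample has been taken and the subject and Investigator have chosen, so some interval at the assigned dose can fall between the failure date and the first rescue dose. Under the rule as written, that interval counts as time to re-suppression on rescue, and a low value obtained within it counts as a rescue response.

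The SAP plans no inference, so the descriptive summaries are the result. A summary that does not measure what its title states has no test or model behind it to expose the discrepancy.

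**Working it through.** **Step 1. Which definition applies.** The references in SAP 8.2.2 can be set against the sections that actually hold each definition.

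| Section | Cites | For | Actual place |
|---|---|---|---|
| 8.2.2.1 | 7.5.6 | virologic failure | 7.5.4 |
| 8.2.2.2 | 7.5.7 | time to failure | 7.5.5 |
| 8.2.2.4, 8.2.2.6 | 7.5.8 | re-suppression | 7.5.6 |
| 8.2.2.5 | 7.5.9 | time to re-suppression | 7.5.7 |
| 8.2.2.7 | 7.5.10 | time after ART restart | 7.5.8 |

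Every reference is two too high. That 8.2.2.5 means 7.5.7 is therefore an inference, but a firm one.

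**Step 2. Time added before rescue.** The plan states no figure to reproduce. Let day 0 be the failure date, g the days from failure to first rescue dose, and r the days from first rescue dose to the first value below 50. Neither g nor r is in the documents; both are assumed. Dosing is weekly with a window of 3 days either way (SAP 2.3), so a move at the next weekly dose, if failure was confirmed on a dosing day, would give g of 4 to 10. I also show 14.

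- SAP 7.5.7: (g + r) − 0 + 1 = g + r + 1
- From first rescue dose: r + 1
- Difference: exactly g days per subject

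| g | r = 14 | r = 28 | r = 56 |
|---|---|---|---|
| 0 | 15 v 15 | 29 v 29 | 57 v 57 |
| 4 | 19 v 15 (+27%) | 33 v 29 (+14%) | 61 v 57 (+7%) |
| 7 | 22 v 15 (+47%) | 36 v 29 (+24%) | 64 v 57 (+12%) |
| 10 | 25 v 15 (+67%) | 39 v 29 (+34%) | 67 v 57 (+18%) |
| 14 | 29 v 15 (+93%) | 43 v 29 (+48%) | 71 v 57 (+25%) |

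Each cell gives the SAP time, then the time from first rescue dose, in days.

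**Step 3. A value drawn before rescue.** Suppose an extra draw on day 5 is below 50 and the first rescue dose is on day 7. SAP 7.5.7 gives 5 − 0 + 1 = 6 days, and 7.5.6 counts the subject as re-suppressed. Measured from the rescue dose the result is 5 − 7 + 1 = −1, so the event came before the treatment it is credited to.

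**Step 4. The ART version.** The end rule is the same, so the same dates with ART restarted on day 7 also give −1. A longer path is foreseen by Protocol 4.2, which lets rescue run until a further failure after re-suppression. Suppose a subject is below 50 on rescue on day 35, fails again, restarts ART on day 134 and is below 50 on day 162. If failure in 7.5.8 means the first failure, the time is 35 − 134 + 1 = −98 days. Counting only values after ART restart, it is 162 − 134 + 1 = 29 days. The SAP does not say which failure is meant.

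**Step 5. Rescue without confirmed failure.** A subject who qualifies by the other route in the rescue note has no failure date under 7.5.5, so 7.5.7 cannot be computed. A start at the first rescue dose exists for every rescued subject.

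**The case against.** The start dates can be defended from the titles. The ART outcome is worded as time after ART re-initiation. The rescue outcome is worded as time for subjects who moved up, which names a subset and not a time zero. The study objective is a treatment strategy, and time from failure answers a strategy question: how long a failing subject stays unsuppressed when offered escalation. This stands. Time from failure is legitimate and should be kept.

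A reader might also infer that the different start dates in 7.5.7 and 7.5.8 bias a comparison of rescue with return to ART. The documents do not support that. No such comparison is planned and no inference is planned at all. The rescue outcome belongs to the Treatment Phase and the ART outcome to the Follow-up Phase. The groups are self-selected and can overlap. RNA is sampled every 2 and later about every 4 weeks on treatment, against every 4 weeks (±7 days) in follow-up. Aligning the start dates would not make the two times comparable. Nor is 7.5.8 a sound model to copy, since its end rule has the same gap.

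Three further points limit the concern. The title of 8.2.2.4 already places re-suppression after the move, so a careful programmer might add the condition unprompted; the definition still does not. A fall from two values of at least 200 to below 50 before escalation may be rare, and the documents give no frequency. Protocol 4.2 offers Part 2 only after virologic failure, so the group without a failure date may be empty, although the outcome note admits it.

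**Conclusion.** The point holds as a gap in definition. For 8.2.2.4 and 8.2.2.5 the SAP supplies no rule tied to the start of the higher dose. Read literally, the general rules can credit rescue with an earlier value, add the wait before escalation to each rescued subject's time, and leave some subjects without a start date. For 8.2.2.7 the end rule allows negative times.

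The added time equals the switch delay, which the documents do not state. The 14% to 48% range assumes a 4 to 14 day delay and 28 days on rescue; over the wider grid above the range is 7% to 93%, and it is zero with no delay. These figures illustrate the formula and do not estimate what the trial will show. The link from 8.2.2.5 to 7.5.7 is inferred from the constant numbering offset.

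No test, power or sample size depends on this. It should not be read as showing that starting at failure is wrong, or that rescue is disadvantaged against ART. What is gained is that each summary measures what its title states. It is a minor correction to listed primary efficacy outcomes.

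**What to change.** 1. Add a rescue-specific definition for 8.2.2.4 and 8.2.2.5. The event is the first RNA below 50 copies/mL in a sample drawn after the first rescue dose, excluding same-day samples taken before the injection. Time is the date of that sample minus the date of the first rescue dose, plus 1. Report time from virologic failure as a second row for subjects who have a failure date.
2. In 7.5.8, count only the first RNA below 50 copies/mL after ART re-initiation.
3. Correct the section references throughout 8.2.2.

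Sections 7.5.6 and 7.5.7 can stay as the general definitions for all subjects with virologic failure, as 8.2.2.6 needs.

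The cost is SAP wording and a small programming change. The first rescue-dose date is already needed for duration at the rescue dose in SAP 8.1.6, and the ART re-initiation date is already used in 7.5.8. If draw and injection times are not recorded, requiring a later calendar date than the first rescue dose settles the same-day case without new data.

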**Table 4-5: Part 2: Single-Arm, Open-label Treatment Phase [Group A]**

Study Drug	Dosage Form	IP concentration	Dosing Frequency and Amount	Route of Administration
PRO 140 525mg	Parenteral solution	175 mg/mL	2 injections of PRO 140 (2 X 1.5 mL/inj.) up to Week 48	SC injection

As shown in [Table 4-6](#), Group B subjects that elect to participate in Part 2 of Treatment Phase after experiencing virologic failure during Part 1 of Treatment Phase will receive PRO 140 700mg SC weekly injection for remainder of 48-week Treatment Phase. Should subject experience subsequent virologic failure in Part 2 of Treatment Phase, subject will complete Virologic Failure (VF) Visit assessments and then enter the Follow-up Phase of the study.

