**Table 4-6: Part 2: Single-Arm, Open-label Treatment Phase [Group B]**

Study Drug	Dosage Form	IP concentration	Dosing Frequency and Amount	Route of Administration
PRO 140 700mg	Parenteral solution	175 mg/mL	2 injections of PRO 140 (2 X 2 mL/inj.) up to Week 48	SC injection

Group A or Group B subjects that do not elect to participate in Part 2 of Treatment Phase and all Group C subjects who experience virologic failure (defined as two consecutive HIV-1 RNA levels of  $\geq 200$  copies/mL) at any time during the Treatment Phase will undergo the Virologic

Failure (VF) Visit assessments and then exit the Treatment Phase to enter the Follow-up Phase of the study.

Subjects who do not experience virologic failure will enter the Follow-up Phase of the study at the end of 48-week Treatment Phase.

All study subjects will re-initiate their previous antiretroviral regimen or an alternative regimen selected by their treating physician:

- One week prior to the end of 48-week Treatment Phase, or
- Anytime during the Treatment Phase, if virologic failure occurs or have met any other criteria for discontinuation of study treatment as specified in [Section 5.2.1](#) of the protocol. Subjects will be allowed to continue PRO 140 monotherapy while waiting for new ART regimen to be constructed by the Investigator.

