2.2 Design Overview

This study is a Phase 2b/3, multi-center, randomized, two-part, open-labeled study designed to evaluate safety and tolerability of the strategy of shifting clinically stable patients receiving suppressive combination antiretroviral therapy to PRO 140 monotherapy and maintaining viral suppression for 48 weeks following study entry.

Consenting patients will be shifted from combination antiretroviral regimen to weekly PRO 140 monotherapy for 48 weeks during the Treatment Phase with the one week overlap of existing retroviral regimen and PRO 140 at the beginning of the study treatment and also one week overlap at the end of the treatment in subjects who do not experience virologic failure. The first ~150 eligible subjects were enrolled to receive PRO 140 350mg SC weekly injection in a single-arm study. Subsequently, next ~150 subjects were randomized 1:1 to PRO 140 350mg (Group A) or PRO 140 525mg (Group B). An additional ~200 subjects will be randomized 1:1 to PRO 140 525mg (Group B) or PRO 140 700mg (Group C).

➤ **For the first ~150 enrolled subjects:**

- **Part 1:** 48-week, single-arm, open-label treatment phase
 - PRO 140 350mg SC weekly injection (Group A)

➤ **For the subsequent ~150 enrolled subjects:**

- **Part 1:** 48-week, randomized, two-arm, open-label treatment phase
 - PRO 140 350mg SC weekly injection (Group A)
 - PRO 140 525mg SC weekly injection (Group B)

➤ **For the subsequent ~200 enrolled subjects:**

- **Part 1:** 48-week, randomized, two-arm, open-label treatment phase
 - PRO 140 525mg SC weekly injection (Group B)
 - PRO 140 700mg SC weekly injection (Group C)

As noted below, subjects in Group A or Group B that experience virologic failure prior to week 48 in Part 1 have option of entering Part 2 wherein they receive higher dose of PRO 140 for remainder

of treatment phase or may re-initiate prior ART regimen (or an alternative regimen selected by their treating physician) at the discretion of the subject and Investigator.

Part 2 – Rescue Arm for Group A and Group B subjects

- **Part 2 for Group A:** single arm, open-label treatment phase for Group A subjects electing to receive PRO 140 525mg SC after experiencing virologic failure on 350mg SC/weekly dose
- **Part 2 for Group B:** single arm, open-label treatment phase for Group B subjects electing to receive PRO 140 700mg SC after experiencing virologic failure on 525mg SC/weekly dose

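### SAP 7.5.8 times re-suppression from ART restart but does not require the RNA <50 value to come after the restart, so some subjects get zero or negative times

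*SAP*

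**What the plan says.** SAP 7.5.8 covers subjects who fail and then go back on oral therapy: "This will be assessed for all subjects experiencing virologic failure and oral combination antiviral therapy is re-initiated". Its event sentence is the one already used in 7.5.7: "The date of viral re-suppression is defined as the date of first assessment where plasma HIV-1 RNA levels of <50 copies/mL after virologic failure". Only the starting date differs. In 7.5.7 it is the failure date; in 7.5.8 it is the restart date, giving "Date of first HIV-1 RNA levels of < 50 copies/mL – Date of first re-initiation of oral combination regimen) +1".

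SAP 8.2.2.7 summarises the result by treatment group as n, mean, SD, median, minimum and maximum in the "subset of the ITT and PP populations that experienced virologic failure and had re-initiation of oral combination antiviral therapy". Its heading places the outcome after ART restart in the Follow-up Phase. It cites Section 7.5.10, which does not exist. The other 8.2.2 references to 7.5 are two numbers too high as well, so 7.5.8 is clearly meant.

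The design lets RNA fall below 50 before ART restarts. SAP 2.2 provides a "Rescue Arm for Group A and Group B subjects", and re-suppression on that higher dose is a primary efficacy outcome of its own (SAP 3.1.2). Under the Notes in Protocol 4.2, rescue treatment runs for the rest of the 48 weeks "or until subsequent virologic failure event after viral re-suppression on higher dose". After a second failure in Part 2, the "subject will complete Virologic Failure (VF) Visit assessments and then enter the Follow-up Phase of the study". Failures in Groups A and B who decline Part 2, "and all Group C subjects who experience virologic failure", go straight to the VF Visit and Follow-up. Protocol 4.2 has all subjects restart ART, either one week before the end of treatment or on failure or another reason for stopping. It also lets them stay on PRO 140 while a new regimen is put together.

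**The concern.** The clock and the event belong to different questions. The clock starts at ART restart; the event can happen at any time after failure, on any treatment. A subject who re-suppressed on the rescue dose months before restarting ART meets every condition of 7.5.8 and contributes a date that has nothing to do with ART.

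The outcome is meant to show how quickly people who lose control on monotherapy regain it on oral therapy. That is a central safety question for this strategy, and Protocol 8.5 and 12 have the DMC follow re-suppression after oral therapy resumes. A table that mixes in rescue-dose dates, or credits ART with subjects who were already suppressed, does not answer it.

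**Working it through.** The documents give no figure to reproduce. The check is date arithmetic on the 7.5.8 formula, with D50 the first RNA <50 after failure and DART the restart date:

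time = (D50 - DART) + 1

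**Threshold**

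| D50 - DART (days) | Time (days) |
|---|---|
| +28 | 29 |
| 0 | 1 |
| -1 | 0 |
| -2 | -1 |
| -28 (4 weeks) | -27 |
| -84 (12 weeks) | -83 |

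**Example subjects.** The visits are my assumptions, at nominal weekly spacing, so visit Tn falls on day 7(n - 1) + 1: T8 = day 50, T12 = 78, T26 = 176, T47 = 323.

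- *Subject 1, Group A or B.* Failure confirmed at T8, rescue dose, first RNA <50 at T12, no second failure, ART restart at T47. SAP 7.5.7 gives 78 - 50 + 1 = 29 days, which is sensible. SAP 7.5.8 gives 78 - 323 + 1 = -244 days.
- *Subject 2, Group A or B.* As above to T12, then a second failure and ART restart at T26, and RNA <50 again 28 days later (day 204). Dated from the first failure: 78 - 176 + 1 = -97 days. Dated from the second: 204 - 176 + 1 = 29 days. The SAP does not say which failure counts.
- *Subject 3, any group, never rescued.* ART restarted on the failure date, RNA <50 28 days later: 28 + 1 = 29 days. No problem.
- *Subject 4, any group including C.* Stays on PRO 140 while a regimen is put together and has a first RNA <50 seven days before restart: -7 + 1 = -6 days.

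**Does the Follow-up Phase wording in the 8.2.2.7 heading settle it?** It is in neither the definition nor the subset.

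- If it limits *subjects*, Subject 2 still qualifies, because a second failure leads into Follow-up, and the -97 stands if the first failure is used.
- If it limits *RNA values*, Subject 1's first Follow-up value, if <50, gives an ordinary positive time. ART is then credited with re-suppressing someone already below 50 at restart.

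**Illustrative effect on a group mean.** Assume a share p of the row had RNA <50 g weeks before restart. Assume the rest take 29 days, that is, ART restarted on the VF Visit date and RNA <50 at the first follow-up visit four weeks later. Then

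mean = (1 - p) x 29 + p x (-7g + 1)

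For p = 10% and g = 4: 0.90 x 29 + 0.10 x (-27) = 26.1 - 2.7 = 23.4 days.

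| Share p | g = 4 weeks | g = 12 weeks |
|---|---|---|
| 5% | 26.2 | 23.4 |
| 10% | 23.4 | 17.8 |
| 25% | 15.0 | 1.0 |

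Neither p nor g is given in the documents. The median may not move.

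**The case against.** The best defence is that the intent is plain. The 7.5.8 title, its result label, the outcome name in 3.1.2 and the 8.2.2.7 heading all speak of re-suppression after ART restart. The event sentence looks carried over from 7.5.7. A negative time contradicts its own label and would show in the minimum. There is no inference or imputation (SAP 7.3, 7.4), and all data are listed (SAP 8). All of that stands and limits the damage. It does not change what the operative definition tells a programmer to compute. Nor does it help where the heading is read as limiting RNA values, because those times look normal and only the listings would reveal them.

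A reader might also infer more than the documents support:

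- *That the reported mean will be badly distorted.* The documents give no rate of rescue uptake, of re-suppression on rescue, or of the delay to ART.
- *That a specific spurious time follows for rescue responders from the Follow-up visit schedule.* Protocol Table 4-3(a) is for subjects without virologic failure, and Table 4-3(b) counts from the VF Visit. The synopsis ties virologic-failure follow-up to Group C and to Group A and B subjects outside Part 2. The schedule for a rescue responder is therefore not settled.
- *That the rescue outcomes in 8.2.2.4 and 8.2.2.5 are equally contaminated.* Their headings confine them to the Treatment Phase. After a Week-47 restart, T48 is the only scheduled RNA test left in it.

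**Conclusion.** The point holds. SAP 7.5.8 is a stated rule that gives a wrong result for a foreseeable path through the trial. The time is 0 when the first post-failure RNA <50 comes one day before ART restart, and negative at two or more days. Rescue-dose responders in Groups A and B are the main case. It would be wrong to call Group C immune: it has no rescue arm, but continuing PRO 140 while a regimen is put together can produce the same pattern.

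The conclusion rests on the text of 7.5.8 and 8.2.2.7 and on Protocol 4.2 giving all subjects an ART restart. The number affected is unknown, and the means above are illustrations, not estimates. Because the analyses are descriptive and the dates are listed, the right answer can be recovered, but it should be specified in advance.

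**What to change.** In SAP 7.5.8 and 8.2.2.7:

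- Define the event as the first RNA <50 after the ART restart date. The smallest possible time is then 1 + 1 = 2 days.
- Restrict the analysis to virologic failures with RNA at or above 50 on the last test before restart, counting a same-day sample as before restart.
- Report subjects already below 50 at restart separately, with counts by group.
- State that for a subject with two failures, the one preceding ART restart applies.
- Replace the reference to 7.5.10 with 7.5.8.

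Under these rules Subject 1, if still below 50, moves to the separate count, Subject 2 has 29 days, and Subject 3 is unchanged. It is also worth noting in 8.2.2.4 and 8.2.2.5 that a T48 RNA taken after a Week-47 restart is not rescue-dose re-suppression.

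Separately, the passages on rescue-arm subjects need to be reconciled. Protocol 4.2 has all subjects restart ART a week before the end of treatment, while Sections 3 and 7.5.1 describe that overlap for subjects without virologic failure. The synopsis and Table 4-3 leave the follow-up schedule of rescue responders unclear. No clinical rule is proposed here.

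The cost is SAP wording and a little programming on dates already collected. The downside is a smaller analysed group and possibly less favourable figures.
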